### **4.3 Life Style Guidelines**

Patients who are biologically capable of having children and sexually active must agree to use an acceptable method of contraception for the duration of the treatment period and for at least 6 months after the last dose of study treatment. The investigator will counsel the patient on selection of contraception method and instruct the patient in its consistent and correct use. Examples of acceptable forms of contraception include:

1. Oral, inserted, injected or implanted hormonal methods of contraception, provided it has been used for an adequate period of time to ensure effectiveness.
2. Correctly placed copper containing intrauterine device (IUD).

3. Male condom or female condom used WITH a spermicide.
4. Male sterilization with confirmed absence of sperm in the post-vasectomy ejaculate.
5. Bilateral tubal ligation or bilateral salpingectomy.

The investigator will instruct the patient to call immediately if the selected birth control method is discontinued or if pregnancy is known or suspected.

Note: Women are considered post-menopausal and/or not of child bearing potential if they have had 12 months of natural (spontaneous) amenorrhea with an appropriate clinical profile (e.g., age appropriate, history of vasomotor symptoms) or have had surgical bilateral oophorectomy (with or without hysterectomy) or tubal ligation at least 6 months ago. In case of any ambiguity, the reproductive status of the woman should be confirmed by hormone level assessment.

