- 5 Pregnancy Test: If the patient is a woman of childbearing potential, negative serum or urine pregnancy test performed by the local laboratory at screening will be required. The informed consent process must include discussion of the risks associated with pregnancy and adequate contraception methods. Additional pregnancy testing may be necessary if required by local practices or regulations, or if potential pregnancy is suspected.
- 6 Selected Lead-In, Day 1 Assessments: Repeat assessment not required if screening assessment performed within 7 days before the first dose.
- 7 Safety Laboratory Assessments: Hematology, coagulation, chemistry and thyroid function evaluations (see [Section 7.3.4](#)) will be performed by local laboratories. For scheduling convenience, these assessments may be performed one day prior to the visit at the start of the 7-day Lead-in Period and Cycle 1 Day 1.
- 8 Pharmacokinetic Samples: Blood samples to be collected following ECGs and assessment of vital signs as scheduled in [Table 2](#). In addition, in the event of a Serious Adverse Event (SAE), unscheduled PK blood samples should be drawn for each study treatment as soon as possible.
- 9 Anti-Drug Antibody Samples: Blood samples to be collected as scheduled in [Table 2](#).
- 10 Tumor Biopsy for Biomarker Studies: Consent for serial sampling of tumor tissue (preferably the same lesion) is requested but is not mandatory for study entry. The tumor biopsy used to determine eligibility may be used for the baseline assessment. Four collection timepoints are scheduled: baseline, C1D1, C2D1, and EOT. Markers of interest in tumor tissue include PD-L1 expression, CD8+ tumor infiltrating lymphocytes (TILs), natural killer cells (NK-cells), T regulatory cells (Tregs), and myeloid derived suppressor cells (MDSCs). Tumor biopsy tissue samples will not be collected on subjects in the Phase 1 50 mg cohort, and are optional for subjects in all other cohorts.

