  - b. For Phase 2 – Measurable disease, as per RECIST version 1.1. Indicator lesions intended for repeat biopsy during the study should be excluded from selection as target lesions at baseline
6. Eastern Cooperative Oncology Group (ECOG) performance status 0 or 1
7. Adequate bone marrow and organ function demonstrated by:
  - a. Hemoglobin  $\geq$  9.0 g/dL
  - b. Absolute neutrophil count  $\geq$  1,500/mm^3 ( $\geq$  1.5  $\times$  10^9/L)

- c. Platelet count  $\geq 100 \times 10^9/L$  ( $\geq 100,000$  per  $\text{mm}^3$ )
  - d. Alanine aminotransferase (ALT) and aspartate aminotransferase (AST)  $\leq 2.5 \times$  Upper Limit of Normal (ULN), or  $\leq 5.0 \times$  ULN for patients with documented liver metastases
  - e. Serum bilirubin  $\leq 1.5 \times$  ULN or  $\leq 3.0 \times$  ULN for patients with Gilbert Syndrome or documented liver metastases
  - f. Serum creatinine  $\text{CL} > 40$  mL/min by the Cockcroft-Gault formula or by 24-hour urine collection for determination of creatinine clearance
8.  $\geq 18$  years of age
9. Women of child-bearing potential (WOCBP) or men whose partner is a WOCBP agrees to use contraception while participating in this study, and for a period of 6 months following termination of study treatment
10. Completed informed consent process, including signing IRB/EC-approved informed consent form
11. Willing to comply with clinical trial instructions and requirements

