#### 5.4.1.3 *Concomitant Medications and Substances to be Avoided On-Study*

Warfarin or Coumarin Derivatives: Therapeutic doses of warfarin or other coumarin derivative anticoagulants are not permitted. Warfarin has a narrow therapeutic range and mocetinostat can have inhibitory effects on CYP2C9, the main metabolizing enzyme of warfarin.

Drugs with QTc Prolonging Activity: As listed in [Appendix 3](#). This list is not exhaustive. Any questions should be discussed with the Sponsor.

Herbal Medications/Preparations: Herbal medications and preparations are not allowed throughout the study, as a potential drug-drug interaction is always possible. These herbal medications include, but are not limited to: St. John's wort, Kava, ephedra (ma huang), ginkgo biloba, dehydroepiandrosterone (DHEA), yohimbe (yohimbine), saw palmetto, and ginseng. Patients should stop using these herbal medications at least 7 days prior to first dose of study treatment.

Gastric Acid Neutralizers: Medications that directly increase gastric pH such as short-acting antacids should be avoided 4 hours before and 2 hours after administration of mocetinostat. Medications that affect gastric acid secretion, such as H2 antagonists or proton pump inhibitors should be avoided.

Contraceptives: Hormonal contraceptives may be affected by cytochrome P450 interactions, and are therefore not considered effective for this study, since induction of CYP3A4 may not be excluded in patients receiving mocetinostat.

Immunosuppressive Medications: Including, but not limited to systemic corticosteroids at doses not exceeding 10 mg/day of prednisone or equivalent, methotrexate, azathioprine, and TNF- $\alpha$  blockers. Use of immunosuppressive medications for the management of investigational product-related AEs or in patients with contrast allergies is acceptable. In addition, use of inhaled and intranasal corticosteroids is permitted. A temporary period of steroids will be allowed for different indications, at the discretion of the principal investigator (e.g., chronic obstructive pulmonary disease, radiation, nausea, etc).

Vaccines: Live attenuated vaccines within 30 days of durvalumab dosing are to be avoided (i.e., 30 days prior to the first dose, during treatment with durvalumab and for 30 days post discontinuation of durvalumab). Inactivated vaccines, such as the injectable influenza vaccine, are permitted.

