**Table 13: Laboratory Safety Parameters**

Hematology Panel	Blood Chemistry Panel
Hemoglobin	Aspartate aminotransferase (ALT)
Platelet count	Alanine aminotransferase (AST)
White blood cell count (WBC)	Alkaline phosphatase
Neutrophil count	Lactate dehydrogenase (LDH)
Lymphocyte count	Total bilirubin (if Total bilirubin is $\geq 2 \times$ ULN and no evidence of Gilbert's syndrome, then fractionate into direct and indirect bilirubin)
Basophil count	Gamma glutamyltransferase Screening, C1D1, and as clinically indicated
Monocyte count	Lipase
Eosinophil count	Amylase
Coagulation	Creatinine
International normalized ratio (INR)	Blood urea nitrogen (BUN) or urea, depending on local practice
Prothrombin time (PT)	Uric acid
Partial thromboplastin time (PTT)	Total protein
	Glucose (non-fasted)
Urinalysis (dip stick)	Albumin
Blood	Calcium
Glucose	Sodium
Protein	Potassium
	Chloride
Thyroid Function Test	Magnesium
Thyroid-stimulating hormone (TSH)	Bicarbonate [ $\text{CO}_2$ ]
Free-T3 (if TSH abnormal)	
Free-T4 (if TSH abnormal)	

Pregnancy Testing: For patients of childbearing potential, a serum or urine pregnancy test will be performed at screening. Pregnancy tests will also be done whenever pregnancy is suspected during the study. Additional pregnancy testing may be necessary if required by local practices or regulations.

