### **8.3.2 Exposure During Pregnancy**

Exposure during pregnancy (i.e., exposure in-utero [EIU]) may occur in a female study participant, the female partner of a male study participant or study site personnel working with the investigational product (e.g., occupational exposure) if:

- A female becomes or is found to be pregnant during treatment or within 6 months after discontinuing treatment or having been directly exposed to the investigational product;

- A male is exposed to the investigational product prior to or around the time of conception or during the pregnancy of his partner.

If exposure in-utero occurs, the investigator must submit an SAE form and an EIU Supplemental Form within 24 hours of awareness of the exposure, regardless of whether an AE or SAE has occurred.

In the event of pregnancy in a female study participant, if the pregnancy is continued, study treatment will be immediately discontinued.

In the event of exposure of the pregnant partner of a male study participant, the study participant should be asked to deliver an EIU Pregnant Partner Release of Information Form to his partner. The Investigator must document on the EIU Form that the patient was given this letter to provide to his partner.

Follow-up to obtain pregnancy outcome information is to be conducted for all EIU reports. In the case of a live birth, the health of the neonate should be assessed at the time of birth and for up to 3 months after birth. Further follow-up of birth outcomes will be handled on a case-by-case basis (e.g., follow-up on preterm infants to identify developmental delays). In the event the pregnancy is terminated, the reason(s) for termination should be reported and, if clinically possible, the structural integrity of the terminated fetus should be assessed by gross visual inspection.

If the outcome of the pregnancy meets the criteria for an SAE (i.e., ectopic pregnancy, spontaneous abortion, intrauterine fetal demise, neonatal death, or congenital anomaly), an SAE report should be submitted to the Sponsor.

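### Section 4.3 accepts a hormonal contraceptive on its own, but Section 5.4.1.3 says hormonal contraceptives are not considered effective in patients receiving mocetinostat

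*Protocol*

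**What the plan says.** Section 4.3 of the protocol (Life Style Guidelines) says that sexually active patients able to have children "must agree to use an acceptable method of contraception for the duration of the treatment period and for at least 6 months" once dosing has ended. It then lists five examples of acceptable forms. Item 1 is "Oral, inserted, injected or implanted hormonal methods of contraception, provided it has been used for an adequate period of time to ensure effectiveness". Items 2 to 5 are a copper intrauterine device, a condom with spermicide, confirmed male sterilization, and tubal ligation or salpingectomy.

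Section 5.4.1.3, on medications and substances to be avoided on study, raises a possible cytochrome P450 interaction with hormonal contraceptives. It concludes that these products "are therefore not considered effective for this study, since induction of CYP3A4 may not be excluded in patients receiving mocetinostat".

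Inclusion criterion 9 (Section 4.1) requires only that a woman of child-bearing potential, or a man whose partner is one, "agrees to use contraception while participating in this study" and for 6 months afterwards. It names no method.

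On testing, Table 1 schedules one pregnancy test, at screening, and leaves later tests to clinical indication. Footnote 5 adds "Additional pregnancy testing may be necessary if required by local practices or regulations, or if potential pregnancy is suspected". Section 7.3.4 says "Pregnancy tests will also be done whenever pregnancy is suspected during the study". Section 8.3.2 states the response to a pregnancy: "In the event of pregnancy in a female study participant, if the pregnancy is continued, study treatment will be immediately discontinued".

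**The concern.** The two sections give a site different answers about the same method for the same patient. An investigator counselling from Section 4.3 would accept a woman on an established oral contraceptive. The statement that such methods are not considered effective sits in a concomitant-medication section that Section 4.3 never mentions.

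What is at stake is fetal exposure. The reporting, testing and discontinuation rules find a pregnancy or respond to it; they do not prevent one. During treatment, prevention depends mainly on the contraceptive method, and Section 4.3 allows one that the protocol elsewhere says cannot be relied on.

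**Working it through.** The plan states no figure on this point, so the check compares the texts.

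1. **How many methods are required?** Section 4.3 asks for an acceptable method, in the singular. Where the list intends a combination it says so: item 3 reads "Male condom or female condom used WITH a spermicide". Item 1 has no such wording. A hormonal method alone therefore satisfies Section 4.3.

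2. **What condition does item 1 carry?** Only that the method has been used for long enough. That concerns duration of use, not drug interaction. A woman who has taken an oral contraceptive for years meets it on her first day of mocetinostat.

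3. **Who is covered by Section 5.4.1.3?** Its reason is possible CYP3A4 induction in patients receiving mocetinostat. It applies to female participants taking the drug, and not to female partners of male participants.

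4. **Do the sections conflict for that group?** Yes. For a woman on mocetinostat, a hormonal method is acceptable under 4.3 and not effective under 5.4.1.3.

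5. **Does other text reconcile them?** No.
   - Criterion 9 names no method and excludes none.
   - Table 1 footnote 5 requires the consent discussion to cover adequate contraception, without saying which methods qualify.
   - Section 1.2.4 says mocetinostat does not appear to be a strong inducer of CYP enzymes. That is compatible with induction not being excluded, and it does not withdraw Section 5.4.1.3.
   - SAP Section 12.6.14 repeats the testing rules and plans only a listing of results.

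6. **Counts.** Methods listed in Section 4.3: 5. In conflict with Section 5.4.1.3: 1 (item 1). Satisfying both sections: 5 − 1 = 4 (items 2 to 5). Routinely scheduled pregnancy tests: 1 at screening and 0 during treatment.

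**The case against.** The strongest reply is that the protective rule is already written. Section 5.4.1.3 is specific, gives its reason and binds sites as much as Section 4.3. The list in 4.3 consists of examples for all patients able to have children, including men whose partners take no mocetinostat, so item 1 has a legitimate use. A site can comply with both sections by choosing from items 2 to 5. Item 1 also mentions effectiveness, the investigator must counsel on choice of method, and the consent discussion must cover contraception. The size of the risk is unknown: Section 1.2.4 suggests mocetinostat is not a strong inducer, and Section 5.4.1.3 speaks only of induction that may not be excluded.

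Parts of this stand. The risk cannot be quantified from the documents. The option is sound for partners. Consent pages are not in the public copy, so what patients are told about hormonal methods cannot be checked. Testing after screening may also follow any clinical indication, not only suspected pregnancy.

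None of it removes the conflict. The examples are examples of acceptable forms, and counselling under Section 4.3 draws on that same list. The effectiveness wording in item 1 is tied to duration of use. Section 4.3 does not limit item 1 to partners, and nothing in it tells a site that item 1 alone is insufficient for a woman on study drug. Testing as clinically indicated still leaves no routine test on treatment.

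**Conclusion.** The concern holds. Section 4.3 item 1 is wrong as written for women of child-bearing potential receiving mocetinostat, because it accepts as a sole method something Section 5.4.1.3 says is not considered effective for this study. It is an internal inconsistency bearing on patient safety and should be corrected. It does not touch endpoints, sample size or analysis.

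The extent is one of five listed methods, with no routine on-treatment pregnancy test behind it. The number of women who would rely on a hormonal method alone is not given, and the documents do not show whether induction occurs or how large it would be. The conclusion assumes that the sponsor still holds the position in Section 5.4.1.3. It is limited to the time on mocetinostat, because the documents do not say how long any induction would last after the last dose.

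**What to change.** Amend Section 4.3 item 1 to say that, for women receiving mocetinostat, a hormonal method alone is not sufficient and a non-hormonal method from items 2 to 5 must be used, alone or in addition. Cross-refer to Section 5.4.1.3. Keep the hormonal option for female partners of male participants. The sponsor should also say whether the restriction continues after mocetinostat stops, including for a woman who stays on durvalumab, since Section 4.3 requires contraception for at least 6 months after the last dose of study treatment.

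If the sponsor's clinical pharmacology staff conclude that CYP3A4 induction is excluded, withdraw the statement in Section 5.4.1.3 instead. Section 1.2.4 needs no change for the recommended wording.

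The drafting cost is a sentence or two and a cross-reference, by administrative letter or with the next amendment. Under Section 13.1 either route needs IRB/EC approval before it takes effect, and the consent form may need a matching edit. There is no cost to sample size or analysis.

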#### **4.4 Enrollment into Study**

Evaluation of tumor PD-L1 expression for Phase 2 patients naïve to treatment with immunotherapy may have been performed historically or more recently for the purpose of determining enrollment into Cohort 1 or 2 of this study. A 14-day turn-around time should be expected from the time of receipt of adequate samples at the central lab to test results returned to the study site. Questions concerning adequacy of samples will cause delay beyond this timeframe.

Following completion of the study-specific informed consent process and review of all screening procedures, patient eligibility will be confirmed by appropriately qualified staff at the investigational site. Patients will be enrolled by entry into a patient registration log provided by the Sponsor and maintained by the study site, and completion of the patient registration procedure detailed in the Study Manual. Each patient will be assigned a sequential number by the study site. The patient number must be used on all documentation and correspondence with the Sponsor, Contract Research Organization (CRO) and laboratory vendors.

## **5 STUDY TREATMENT**

### **5.1 Mocetinostat Study Drug Management**

#### **5.1.1 Formulation and Packaging**

Mocetinostat study drug contains the free-base form of mocetinostat (MGCD0103) and inert excipients: microcrystalline cellulose, sodium starch glycolate, colloidal silicon dioxide, non-bovine magnesium stearate.

Mocetinostat hard gelatin capsules will be supplied by the Sponsor. Capsule strengths to be used in this study are 10 mg (white opaque capsule), 20 mg (white opaque capsule), 25 mg (Swedish orange capsule), and 50 mg (Swedish orange capsule). Refer to the Pharmacy Manual for details on number of capsules per bottle, and clinical trial material supply, distribution and control.

Medication labels comply with the legal requirements of the United States and will be printed in the languages required in the countries in which the study is conducted.

#### **5.1.2 Drug Storage and Accountability**

Mocetinostat capsules should be stored protected from light, at room temperature (suggested range is 15-30°C, 59-86°F) according to instructions on the label. The storage area should be secure with limited access and monitored for temperature using a calibrated thermostat. Shelf-life evaluation of the intact bottles is ongoing. Available stability data support  $\geq 12$ -months shelf-life when stored under the above conditions, depending on capsule strength.

All study treatment supplies will be accounted for in the drug accountability inventory forms supplied by the Sponsor or using locally approved forms that include all required information. The drug accountability inventory forms must identify the study drug, including batch or lot numbers and account for its disposition on a patient-by-patient basis, including specific dates and quantities. The forms must be signed by the individual who dispensed the drug.

#### **5.1.3 Preparation and Dispensing**

Only qualified personnel who are familiar with procedures that minimize undue exposure to them and to the environment should undertake the preparation, handling, and safe disposal of chemotherapeutic agents.

Study site personnel should dispense to patients the appropriate number of capsules required to support one 28-day cycle (12 doses) plus one dose. Mocetinostat capsules are to be dispensed in the Sponsor provided High-Density Polyethylene (HDPE) bottles along with a provided desiccant packet.

### **5.1.4 Medication Compliance**

Study site personnel should provide each patient with written dosing information for mocetinostat capsules and review it with the patient during clinic visits. Patients will be asked to record their daily mocetinostat dosing on Sponsor provided diary cards and report any missed doses or lost capsules at the next clinic visit. Patients will also be told to bring study treatment capsule bottle(s) (empty or not) with them to the clinic visit for a compliance check and capsule count. Study site personnel will record compliance information in the source document and on the CRF and retain the bottle(s) until a monitor has completed reconciliation.

See the Study Manual for additional details regarding compliance and reconciliation.

### **5.1.5 Destruction**

At the end of the study, all unused mocetinostat drug supplies will be destroyed in accordance with local Standard Operating Procedure provided to the Sponsor for the Trial Master File, or returned to the Sponsor or its appointed agent, as directed by the Sponsor.

### **5.1.6 Administration**

Mocetinostat capsules will be administered orally on a three times per week dosing schedule, in 28 day cycles. The starting dose for mocetinostat in the Phase 1 dose escalation study is 50 mg orally TIW with potential to escalate to 70, and 90 mg TIW. The dose may be deescalated to 40 mg TIW depending on observed safety. The RP2D will be established based on the Phase 1 results.

The following guidelines should be followed for mocetinostat administration:

- Patients should be instructed to take the dose of mocetinostat three days per week (e.g., Monday/Wednesday/Friday), in the morning, at approximately the same time each day.
- Mocetinostat should be taken on an empty stomach (e.g., after an overnight fast or at least 3 hours since the previous meal) and wait at least 2 hours before eating the next meal.
- Capsules should be taken with at least 200 mL (7 oz.) of water.
- Patients should swallow the capsules whole and not chew them.
- If vomiting occurs after dosing, mocetinostat doses should not be replaced. If vomiting occurs on a day when PK collection is required, PK samples should continue to be collected.

- Mocetinostat doses should not be taken 2 days in a row and gaps longer than 3 days (~72 hours) should be avoided when possible.

On days mocetinostat and durvalumab are both administered and scheduled for PK assessment, mocetinostat dosing and sampling should precede durvalumab. Mocetinostat dosing should occur in the clinic at each visit where Mocetinostat PK collection is scheduled, but there are no dosing time restrictions on non-PK days (e.g. C2D15, C4D1, C5D1). Cycle 1 Day 15 Mocetinostat dosing must occur at the clinic but all other Day 15 Mocetinostat dosing can be done at home or at the clinic.

